The AirFit F40 is a minimal contact FFM manufactured by ResMed (San Diego, CA) that rests softly and securely under the patients nose and is designed to let patients sleep in any position and move freely throughout the night. The mask consists of three cushion sizes and three headgear sizes. Headgear adjustments can be made with magnetic clips that easily snap on and off.

The AirFit F40 MCFFM is for single-patient reuse in the home environment. The mask is intended to be used on patients weighing more than 66lbs (30kg), who have been prescribed non-invasive CPAP or Bi-level positive airway pressure therapy.

Study Objectives

The primary objective of the study is to assess patient preference for the Philips Respironics Amara View MCFFM compared to the competitor ResMed AirFit F40 MCFFM. The secondary

Document ID:	N/A	Document title:	Classification:	For internal use
		Clinical Study Protocol		
Modified:	24Jun2024		Author:	[name]
Version:	1.0		Approvers:	[name]/[name]
Status:	Final		Page:	8 of 29

aim of the study is to compare PAP therapy device data between the two masks. A detailed description of the aims is presented in the following table.

Objectives	Hypothesis	Endpoints
To determine patient preference for the Amara View compared to the AirFit F40 as determined by ratings of mask attributes.	Subjective ratings on mask attributes will tend to be higher for the Amara View mask compared to the ratings for the AirFit F40 mask.	
Comparison in satisfaction ratings between the Amara View and the AirFit F40 will be measured for the following attributes:
 
 • Bed partner satisfaction (overall) • Fit (cushion, headgear, frame, mask overall) • Comfort (cushion, headgear, frame, mask overall) • Ability to maintain a seal during use (seal satisfaction, leak location) • Stability of the mask • Noise level (self, bed partner) • Air venting (self, bed partner) • Comfort of breathing • Sleep quality • Visual appeal • Patient Satisfaction overall (headgear, cushion, frame, mask) 
Difference in NPS between the Amara View and the AirFit F40
 
Differences in ease of use and satisfaction ratings between the Amara View and the AirFit F40
 
 • Mask clips • Mask overall • Assembly (elbow, cushion, frame, tubing quick disconnect, mask clips) • Disassembly (elbow, cushion, frame, tubing quick disconnect, mask clips)

Document ID:	N/A	Document title:	Classification:	For internal use

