Modified:	24Jun2024		Author:	[name]
Version:	1.0		Approvers:	[name]/[name]
Status:	Final		Page:	14 of 29

Selection and Withdrawal of Participants

Number of Subjects

Approximately 40 participants will be enrolled. It is anticipated that approximately 30 participants will complete all study procedures.

Recruitment considerations

As indicated below, eligibility is based on participants being established PAP users, and currently not using a Philips Amara View or ResMed AirFit F40 full face mask. Eligibility criteria will be collected via self-report by the participant.

Inclusion Criteria

- Aged 21-85 years (inclusive)
- Weight >66 pounds/30 kg
- Established on PAP for \geq 90 days at the time of consent
- Currently prescribed and using fixed pressure, Auto CPAP, or Bi-Level therapy on a regular basis (average PAP usage of \geq 4 hours/night, \geq 4 days per week for \geq 3 months)
- Currently using a Full-Face mask
- Able to read, write, speak and understand English
- Willing and able to provide informed consent
- Willing and able to follow instructions and complete all activities required by the study
- Able to remove a sleep apnea mask without assistance

Exclusion Criteria

- Currently using a Philips Resironics Amara View FFM or ResMed AirFit F40 FFM
- Allergy to silicone
- Allergy to latex
- Unique facial features (i.e., deformities of the face and/or head, piercings, etc.) that could interfere with the therapeutic use of this type of mask
- Employee or living with a family member who works for Philips or any company that designs, sells, or manufactures sleep-related products.
- Prescribed oxygen at night or continuously
- Recent eye surgery or dry eyes
- Hiatal hernia
- Excessive reflux
- Impaired cough reflux

Document ID:	N/A	Document title:	Classification:	For internal use
Modified:	24Jun2024	Clinical Study Protocol	Author:	[name]
Version:	1.0		Approvers:	[name]/[name]
Status:	Final		Page:	15 of 29

- Impaired cardiac sphincter function
- Using prescription drugs that induce vomiting
- Currently participating in another interventional research study or planned participation in another interventional clinical research study during the trial period
- Prescribed an ASV (adaptive servo-ventilation) device
- Prescribed mechanical ventilation
- Pre-existing conditions such as bullous lung disease, pathologically low blood pressure, bypassed upper airway, pneumothorax, pneumocephalus, cerebral spinal fluid (CSF) leaks, or cribriform plate abnormalities

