PI or designee will record all reportable events with start dates occurring any time after informed consent is obtained until the last day of study participation. At each study visit, the investigator will inquire about the occurrence of AE/SAEs since the last visit.

If an SAE or UADE occurs, the PI or designee shall complete a Serious Adverse Event or Unanticipated Adverse Device Effect Report and submit to the study sponsor for review as soon as possible (e.g., within 24 hours of awareness) and no later than 3 calendar days after site's awareness of event. As the site gains more information (i.e., admission records, hospital discharge summaries) a new report with the new information should be submitted to the Sponsor. The study sponsor is responsible for conducting an evaluation of the SAE or UADE and shall report the results of such evaluation to the reviewing IRB and other agencies as applicable.

Device Deficiencies

A device deficiency refers to the inadequacy in the identity, quality, durability, reliability, safety, or performance of an investigational device, including malfunction, use errors or inadequacy in information supplied by the manufacturer. All device deficiencies will be documented on the device deficiency tracking form. If the device deficiency led to a UADE, the SAE or UADE Report should be completed as noted above.

If a device deficiency had the potential to lead to a UADE but did not result in one, it should be documented on the device deficiency tracking form and submitted to the study sponsor for review

Document ID:	N/A	Document title:	Classification:	For internal use
		Clinical Study Protocol		
Modified:	24Jun2024		Author:	[name]
Version:	1.0		Approvers:	[name]/[name]
Status:	Final		Page:	20 of 29

as soon as possible (e.g., within 24 hours of awareness) and no later than 3 calendar days after site personnel's awareness of event.

Statistical Methods

Determination of Sample Size

This study is not statistically powered. The sample size of approximately 30 trial completers is considered sufficient to gauge directional trends comparing the two mask designs.

General Considerations

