All variables will be summarized by descriptive statistics. The statistics for continuous variables will include mean, median, standard deviation, minimum, maximum, 95% confidence interval (CI) for the mean, and number of observations. For categorical variables, frequencies and percentages will be presented. All formal analyses will be conducted using SAS®, and statistical comparisons will be considered significant at an alpha of 0.05, with adjustments for multiple comparisons, as applicable. There are no statistical criteria for terminating the study, and any deviations from the original statistical plan will be noted in the analysis report.

Participant Disposition

Participant disposition, including the total number of participants enrolled, randomized, completed and early terminations, will be presented. In addition, a listing will be provided with the reasons for early termination.

Statistical Analyses

Mask attribute ratings, scaled 0-10, will be collected on both the AirFit F40 and the Amara View Full Face masks. Since the study is not statistically powered, the analysis will focus on the effect sizes and confidence intervals of the paired differences between the masks [Amara View – AirFit F40]. The paired t-test and nonparametric Wilcoxon Signed-Ranks test will further evaluate the trends. In cases where one test calculates a p-value below 0.05 and the other indicates a p-value ≥ 0.05 , the distributions of the paired differences will be inspected to determine which method better models the data. Participants will be excluded from the analysis of a given endpoint if they do not contribute a rating for both study masks.

Residual AHI, leak, air pressure, and average adherence will be extracted from the patients' PAP device data, and the paired differences [Amara View – AirFit F40] will be evaluated as described above.

Percentages and exact binomial confidence intervals will be calculated for categorical questions. The McNemar test will compare binary responses where the same questions are answered after the participants try both masks.

Net Promoter Scores (NPS) will be calculated for the question "Would you recommend this (Amara View FFM or AirFit F40) mask to others?" where the percentage of detractors (ratings 0-6) is subtracted from the percentage promoters (ratings of 9 or 10). Ratings of 7-8 will be considered neutral. Relative NPS will be calculated as [Amara View NPS] – [AirFit F40 NPS].

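### Relative NPS is a named endpoint planned as a point difference with no interval; at about 30 pairs its 95% half-width would be roughly 26 to 48 points for within-person correlations up to 0.5 (assumed response shares)

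*Combined protocol and SAP*

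**What the plan says.** In Study Objectives, the endpoints for the preference objective, which is the study's primary objective, include "Difference in NPS between the Amara View and the AirFit F40". The Statistical Analyses section defines each mask's score from the recommendation question, "where the percentage of detractors (ratings 0-6) is subtracted from the percentage promoters (ratings of 9 or 10", with 7-8 counted as neutral. It then gives the comparison: "Relative NPS will be calculated as [Amara View NPS" minus the AirFit F40 score. The NPS paragraph ends there.

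The same section makes provisions for other kinds of data:

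- For the 0-10 attribute ratings, because the study is unpowered, "the analysis will focus on the effect sizes and confidence intervals of the paired differences between the masks", supplemented by the paired t-test and the Wilcoxon signed-rank test. Device data are handled in the same way by cross-reference.
- For categorical questions, percentages with exact binomial intervals.
- For binary responses given on both masks, McNemar's test.

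On who is analysed, it states: "Participants will be excluded from the analysis of a given endpoint if they do not contribute a rating for both study masks". Participant Accountability and Missing Data repeats this restriction for the formal analysis as a whole. On size, Determination of Sample Size states: "The sample size of approximately 30 trial completers is considered sufficient to gauge directional trends comparing the two mask designs".

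**The concern.** The plan's answer to being unpowered is to show effect sizes with intervals. Relative NPS is a named endpoint that does not get one. None of the listed provisions supplies it. The paired-difference interval is for mean ratings, the exact binomial interval is for a single percentage, and McNemar's test is for two categories where NPS has three.

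Followed as written, the report could show one sponsor-versus-competitor number from about 30 people in an open-label study, with nothing to tell the reader how precise it is. The Background section says the results will feed design decisions, and the Ethics and the Publication and Registration sections foresee marketing use. NPS is an easily quoted figure, and a lead of 15-25 points without an interval invites over-reading.

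**Working it through.** **Plan's own figure.** The documents state no precision, standard deviation or power for NPS, so there is nothing to reproduce. The only size given is the number of completers.

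**Inputs**

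- From the documents: n = 30 pairs (Number of Subjects: "It is anticipated that approximately 30 participants will complete all study procedures"), the NPS categories, and the rule that both masks must be rated. The significance level is 0.05; two-sided is assumed, since sidedness is not stated.
- Assumed, because the documents give no values: promoters p = 30-50% and detractors d = 20-35%, the same on both masks; within-person correlation ρ of the scores = 0, 0.3, 0.5 and 0.7.

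**Identity.** Score each person +100 (promoter), 0 (neutral) or -100 (detractor) on each mask. The mean score on a mask is that mask's NPS. When the same people rate both masks, the mean within-person difference therefore equals relative NPS exactly, and its precision is that of a paired mean.

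**Formulas** (scores as +1, 0, -1; multiply by 100 for points)

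- Variance on one mask: v = p + d - (p - d)²
- SD of the paired difference: √(2v(1 - ρ))
- 95% half-width: t(0.975, 29) × SD / √30 = 2.045 / 5.477 × SD = 0.3734 × SD

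Within the assumed ranges v rises with both p and d, so the extremes lie at 30%/20% and 50%/35%.

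- 30%/20%: v = 0.50 - 0.01 = 0.49
- 40%/30%: v = 0.70 - 0.01 = 0.69
- 50%/35%: v = 0.85 - 0.0225 = 0.8275

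**Half-widths in points**

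| p / d | ρ = 0 | ρ = 0.3 | ρ = 0.5 | ρ = 0.7 |
|---|---|---|---|---|
| 30% / 20% | 37.0 | 30.9 | 26.1 | 20.2 |
| 40% / 30% | 43.9 | 36.7 | 31.0 | 24.0 |
| 50% / 35% | 48.0 | 40.2 | 34.0 | 26.3 |

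Worked cell, 40%/30% at ρ = 0.5: SD = √(2 × 0.69 × 0.5) = 0.831, and 0.3734 × 83.1 = 31.0 points. An observed relative NPS of +20 would then have a 95% CI of about -11 to +51.

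**Unequal shares.** A real difference of 20 points means that the shares differ between masks. Take 50%/20% on one (NPS 30, v = 0.61) and 40%/30% on the other (NPS 10, v = 0.69), with ρ = 0.5. The variance of the difference is 0.61 + 0.69 - 2 × 0.5 × √(0.61 × 0.69) = 0.651, the SD is 80.7 points and the half-width is 30.1. The equal-share simplification is not driving the result.

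**Correlation needed for the interval to exclude zero**: ρ > 1 - (difference / half-width at ρ = 0)².

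| Observed difference | 30% / 20% | 50% / 35% |
|---|---|---|
| 15 points | above 0.84 | above 0.90 |
| 20 points | above 0.71 | above 0.83 |
| 25 points | above 0.54 | above 0.73 |

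At correlations up to 0.5, no difference of 15-25 points excludes zero anywhere in the assumed range. Near 25 points this changes at moderately high correlation.

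**The case against.** The study is openly unpowered and looks for directional trends. NPS is one of many items under the preference objective, no decision rule or success criterion rests on it, and no NPS claim is announced. The estimate is unbiased by this omission, and nothing in the plan forbids adding an interval. All of that stands, and it limits how serious the point is. It does not remove it: being unpowered is the plan's own stated reason for concentrating on intervals.

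Three stronger readings are tempting, and the documents do not support them.

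- **That the plan ignores the pairing.** It already restricts each endpoint to participants who rated both masks, so the subtraction is a paired estimate. Only its standard error is missing.
- **That no uncertainty at all would be shown for this item.** The recommendation question is rated 0-10 and could be read as falling under the paired-rating interval; the category percentages could carry binomial intervals. Neither is an interval for relative NPS, but the reader might see some measure of precision beside it.
- **That a lead of 15-25 points is well within chance.** This is fair at 15 points for all but very high correlations. It fails near 25 points: with 30%/20% and a correlation of 0.6 the half-width is 23.4, which would exclude zero.

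**Conclusion.** The point holds as a cheap improvement to the analysis of one endpoint. Relative NPS is planned as a bare difference, and no other provision in the Statistical Analyses section gives it an interval. Under the assumed shares and 30 pairs, the 95% half-width is about 37-48 points at correlation 0, 31-40 at 0.3, 26-34 at 0.5 and 20-26 at 0.7. A difference of 15-25 points is thus usually compatible with no difference unless the within-person correlation is high. These figures illustrate the scale and are not bounds: the shares and correlations are assumptions, and other values would move them. The textual gap does not depend on them.

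**What to change.** Add to the NPS paragraph of Statistical Analyses: each participant is scored +100 (rating 9-10), 0 (7-8) or -100 (0-6) on each mask; relative NPS is reported as the mean within-person difference, Amara View minus AirFit F40, with a 95% CI from the paired t distribution or from a bootstrap that resamples participants. State that the existing both-masks rule applies to this endpoint, so that the two scores come from the same people and the mean difference equals the planned subtraction.

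The cost is one line of text and trivial programming, with no new data and no change of design. The downside is that the reported result will look less certain than a single number.

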Version:	1.0		Approvers:	[name]/[name]
Status:	Final		Page:	11 of 29

Participants will be asked to bring their prescribed mask and PAP device to Visit 1.

The enrolled population will consist of all participants who provide informed consent and meet eligibility requirements.

Mask Fitting and Use

At the initial visit, participants will undergo a fitting of the mask they are randomized to start the study with; either the Amara View or the AirFit F40 mask. Participants will be fit with mask sizes recommended by the clinician. The clinician will use the provided sizing gauges for the Amara View and AirFit F40 masks respectively. Once a mask size is selected for the first study mask, the participant will have pressure applied for up to 15 minutes using his or her own PAP machine at therapeutic pressure, and an assessment of mask fit will be performed. If the participant's PAP device is not available, they will be fitted with the mask and will have a pressure of up to 10 cm H₂O applied (if participants do not know their therapy pressure) for up to 15 minutes using a PAP device provided by the site. A new bacteria filter and tubing will be used and a disinfection log will be maintained when/if study equipment is used by multiple participants. Participants may be fitted with up to three mask sizes for the mask. A Mask Fitting Survey (Appendix IV) will be used to capture the participant's prescribed pressure, mask (cushion/frame) sizes and fitting observations for the first study mask.

After the mask fitting, participants will be given the first study mask to take home and provided with the Instructions for Use. They will be encouraged to use the mask for the full 15-days of the first trial period. Participants will be instructed to contact the site if they have issues with the recommended cushion and/or headgear sizes. Participants may be provided with additional mask components/sizes as needed. Any change to cushion or headgear sizing during the trial will be documented in EDC.

It is anticipated that the consent, eligibility, baseline/demographic data collection, and mask fitting will take approximately 60 minutes to complete.

Follow-Up Data Collection

There will be two follow-up data collections occurring on 15 and 30-days after the baseline visit.

Visit 2

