After the first 15-day trial period with the first study mask, participants will return to the site for their second study visit. Participants will be instructed to bring their PAP device and return the first study mask to the visit.

Participants will complete a mask attributes survey on the first study mask and then they will be fitted with the second study mask. Fitting procedures will follow the same procedure as described above in the baseline visit. After the mask fitting, participants will be given the second study mask to take home and provided with the Instructions for Use. They will be encouraged to use the mask for the full 15 days of the second trial period. Participants will be instructed to contact the site if they have issues with the recommended cushion and/or headgear size as needed.

If participants did not return the first study mask at the second study visit, they will be asked to bring it to the third study visit.

Document ID:	N/A	Document title:	Classification:	For internal use
		Clinical Study Protocol		
Modified:	24Jun2024		Author:	[name]
Version:	1.0		Approvers:	[name]/[name]
Status:	Final		Page:	12 of 29

It is anticipated the survey completion and mask fitting will take approximately 60 minutes to complete.

Visit 3

After the second 15-day trial period with the second study mask, participants will return to the site for the third and final study visit. During this visit, participants will complete a mask-attributes survey on the second study mask and return all study product.

It is anticipated the survey completion and study product return will take approximately 30 minutes to complete.

After participants have completed both study arms, deidentified data from participants' PAP devices will be extracted from the connected device software Care Orchestrator (CO) for Philips device users only. The site coordinator will confirm the data has been uploaded into CO at visits 2 and 3.

Unscheduled Phone Calls

Documentation of unscheduled phone calls will be captured within the EDC.

Conclusion of Participation

Once the participant returns the study mask(s) and completes the survey, their participation in the study will be complete. Participants will be active in the study for approximately 30 days but no more than 60 days after receipt of the first study mask.

Participant Reimbursement

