 - DreamStation Go CPAP, APAP or Auto CPAP
 - Dorma 400 or 500 CPAP or Auto CPAP
 - System One ASV4
 - System One (Q-Series) 50 series CPAP, Auto CPAP, or BiPAP
 - System One (Q-Series) 60 series CPAP, Auto CPAP, or BiPAP
 - C Series ASV, S/T, or AVAPS
 - REMStar SE Auto CPAP

Withdrawal

The term 'discontinuation' refers to the participant's premature withdrawal from the study prior to completing all procedures. Participants may be discontinued from the study for any of the following reasons:

- At the discretion of the PI or his designee, if he believes that continuing with the protocol is not in the best interest or may prove harmful to the participant. Such a decision may be precipitated by adverse events, including fever, nausea, rash, changes in vital signs, or the development of a new medical condition. The investigator will be responsible for making medical/safety decisions regarding the participants continuing in the study.
- At the request of the participant for any reason (or none)
- At the request of the sponsor

Document ID:	N/A	Document title:	Classification:	For internal use
		Clinical Study Protocol		
Modified:	24Jun2024		Author:	[name]
Version:	1.0		Approvers:	[name]/[name]
Status:	Final		Page:	17 of 29

- Non-compliance, as defined by failure to respond to phone and/or email contact after three attempts made by a study representative or failure to attend study appointment(s) (lost to follow-up), or being unwilling/unable to consistently use PAP (at least 4 days per week) along with the provided mask
- If the study mask/s provided is/are found to be inadequate for use (e.g., seal, stability, comfort, air flow, etc.)
- If eligibility status changes during the study and the participant no longer meets inclusion or exclusion criteria

The study team will document whether or not each participant completed the study. If, for any participant, study treatment or assessments were discontinued, the reason will be recorded. No further data will be collected following study withdrawal. Each patient's health care provider will be responsible for follow-up care following study withdrawal with communication from research staff.

Participants may withdraw from the study at any time. Withdrawal from the study will not affect their medical treatment or future participation in a research study.

Treatment of Subjects

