Document ID:	N/A	Document title:	Classification:	For internal use
		Clinical Study Protocol		
Modified:	24Jun2024		Author:	[name]
Version:	1.0		Approvers:	[name]/[name]
Status:	Final		Page:	21 of 29

Participant Accountability and Missing Data

Participants who withdraw from the study will be tabulated with the reasons for the withdrawal. A participant will only be included in the formal statistical analysis if they contribute data for both study masks.

Safety Analysis

Safety evaluations will be performed by recording adverse events at the time originally reported, and they will be followed at regular intervals until resolution or study completion, whichever comes first. Adverse events will be provided in data listings, but no statistical comparisons will be undertaken.

Interim Analysis

No formal interim analysis is planned for this study.

Exploratory Analyses

Various exploratory analyses may be performed, including subgrouping, correlation, regression, and text analytics, in order to investigate the relation between baseline factors and study endpoints. These analyses could support algorithm development or aid in future study design, but they are not required for the final study report.

Case Report Forms

Study-related case report forms (CRFs) and source documentation will be collected and maintained by the sponsor. All such documentation will be kept confidential and stored on a secure server or protected device. Only staff delegated by the PI will have the ability to enter or make changes to the CRFs and source documents.

Quality Control and Quality Assurance

The PI and study personnel will be trained to the study protocol, study product, TMF documents, monitoring plan, CRFs and/or eCRFs, direct data reporting, and all Sponsor expectations, as applicable. Once complete, training and delegations will be documented for PI and study personnel.

Data queries will be addressed by delegated study personnel, and CRF/ eCRFs will be reviewed and signed off by PI prior to study closure. Monitoring will be completed in accordance with US CFR, ICH-E6 GCP Section 6, and ISO 14155:2011 as applicable and as outlined in the monitoring plan.

Monitoring and Monitoring Plan

Onsite and/or remote monitoring will be conducted for this study. Monitoring details will be outlined in the monitoring plan.

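### Withdrawal because a mask performs poorly removes the participant from the both-masks analysis, with no exit rating and no sensitivity analysis, so the completer comparison can shift

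*Combined protocol and SAP*

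**What the plan says.** The Withdrawal section gives its list as optional: "Participants may be discontinued from the study for any of the following reasons". Two of the reasons concern the mask itself: "If the study mask/s provided is/are found to be inadequate for use (e.g., seal, stability, comfort, air flow, etc", and "being unwilling/unable to consistently use PAP (at least 4 days per week) along with the provided mask". The same section adds: "No further data will be collected following study withdrawal".

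The endpoint table under Study Objectives makes fit, comfort, stability and seal rated attributes; the seal item reads "Ability to maintain a seal during use (seal satisfaction, leak location". Ratings are taken twice. At Visit 2, "Participants will complete a mask attributes survey on the first study mask and then they will be fitted with the second study mask"; the second mask is rated at Visit 3. Comparisons between the study masks are listed only for the Day 30 survey (Appendix VI).

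Under Statistical Analyses, a participant without a rating on both masks is dropped from that endpoint. Participant Accountability and Missing Data repeats this for the whole formal analysis: "A participant will only be included in the formal statistical analysis if they contribute data for both study masks".

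There are partial safeguards. Under Mask Fitting and Use, "Participants may be provided with additional mask components/sizes as needed". Reasons for early termination are listed (Participant Disposition) and reasons for withdrawal are tabulated (Participant Accountability and Missing Data). Device deficiencies go on a tracking form. No output is stated to be split by mask or period, and no sensitivity analysis for missing ratings is planned. The exploratory analyses are optional and concern baseline factors.

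**The concern.** The reason a participant leaves can be the quantity being compared. Someone who leaves before the Visit 2 survey has no rating of either mask. Someone who leaves between the Visit 2 and Visit 3 surveys has a first-mask rating, which may enter the descriptive summaries but not the paired analysis; the rating of the mask that failed is never taken. If poor ratings lead to withdrawal, completers are selected for tolerating both masks. The mask that drives more people out for that reason loses more of its low ratings and looks better than it is.

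Determination of Sample Size says the study is meant to gauge directional trends, and Statistical Analyses puts the weight on effect sizes and confidence intervals. Those are the outputs that this selection moves. It does not fade with more completers, and the confidence interval does not reflect it.

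**Working it through.** **Inputs from the documents.** About 40 enrolled and about 30 completers (Number of Subjects); ratings scaled 0-10; estimate = Amara View minus AirFit F40, paired. The two counts agree: implied non-completion is 10/40 = 25%, and 30/(1 - 0.25) = 40. The plan does not say how many of the 10 leave because of a mask. I therefore show 3, 5 and 10 of 40 (7.5%, 12.5%, 25%); 10 is the upper bound.

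**Assumptions, not from the documents.** Means, SDs and the correlation between a participant's two ratings. The simulation uses 1,000,000 correlated pairs, rounded and limited to 0-10, with random mask order. A rating of 4 or below leads to withdrawal with probability p, the same for both masks unless stated. p is set to give the total loss (0.21, 0.35 and 0.75 at correlation 0.3 in the base case). Differences below are worse mask minus better mask. Further losses unrelated to ratings would not change the expected estimate.

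**Base case: means 6 and 7, SD 2.2 each, true difference about -0.94.**

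| Correlation | 3 of 40 | 5 of 40 | 10 of 40 |
|---|---|---|---|
| 0.3 | -0.90 | -0.87 | -0.74 |
| 0.5 | -0.91 | -0.88 | -0.77 |
| 0.7 | -0.92 | -0.90 | -0.80 |

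The shrinkage is 4%, 8% and 22% at correlation 0.3, and 2%, 5% and 15% at 0.7. At 25% loss and correlation 0.3, 17.0% are lost on the worse mask and 8.0% on the other.

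Precision: half-width = 2.045 x SD of completer differences / sqrt(30), which gives 0.91, 0.89 and 0.82 at correlation 0.3, and 0.62, 0.61 and 0.58 at 0.7. The largest shift, 0.94 - 0.74 = 0.20, is well inside these.

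**Where the sign can change (correlation 0.3).**
- Worse mask more variable (means 6.8 and 7, SD 3 and 2): true -0.35; completers -0.24, -0.15 and +0.14 at 3, 5 and 10 of 40. Reversal occurs only at 10, where the half-width is about 0.85.
- Equal SD 2.2, means 6.7 and 7, but withdrawal probability 0.9 on the worse mask and 0.3 on the other (17% lost): true -0.27; completers about +0.03.

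**Equal failure counts (means 6.5 and 7.5, SD 2 and 3, correlation 0.3).** True -0.70; completers about -0.76, -0.80 and -0.91 at 3, 5 and 10 of 40. Balanced counts do not by themselves show that there is no bias.

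**Acceptability composite.** Let L of 30 completers prefer the leading mask, and let a and b be the mask-related withdrawals counted against the leader and against the other mask. The leader's share is (L + b)/(30 + a + b), which is below half when a - b > 2L - 30. With b = 0: L = 16 needs a = 3 (16/33 = 48.5%); L = 17 needs 5 (17/35 = 48.6%); L = 18 needs 7 (18/37 = 48.6%); L = 20 stays at half even with 10 (20/40 = 50.0%). This composite combines preference with withdrawal and is not head-to-head preference.

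**Would a mixed model help?** Base-case means and SDs, 800,000 pairs, p = 0.7, loss driven by the rating of the mask in use, true -0.94:

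| Correlation (lost) | Completers | Model, no exit ratings | Exit uptake 50% | 75% | 100% |
|---|---|---|---|---|---|
| 0.3 (23.6%) | -0.75 | -0.73 | -0.85 | -0.90 | -0.94 |
| 0.7 (21.7%) | -0.84 | -0.81 | -0.88 | -0.91 | -0.94 |

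Under this mechanism the exit ratings remove the bias; the model without them does not.

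**The case against.** The best defence is proportion. The study is not powered, its purpose is feedback to a design team, and with 3 to 5 mask-related withdrawals the base-case shift is a few percent, far inside sampling error. Supplying other sizes should prevent some withdrawals. Randomized sequence and the recorded reason for discontinuation, together with the withdrawal date, would largely identify mask and period, so that split is a table-layout request. All of this stands, and it keeps the severity low. It does not supply the missing rating.

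Several stronger readings are tempting and are not supported:
- That the plan forces poor-mask participants out. The wording is permissive.
- That it forbids an exit survey. The sentence stops collection after withdrawal; the gap is that no survey is scheduled at the withdrawal contact.
- That all 10 expected non-completers will leave because of a mask. The documents give no split.
- That the planned result is likely to point the wrong way. Reversal needs a small true difference plus unequal variability with heavy loss, or unequal withdrawal probabilities. In the unequal-variability example, intervals around both the true and the completer value would include zero.
- That equal SDs protect the sign. They do so in the base case, with its shared threshold and probability and its true difference, but not in general.
- That a 16/30 preference would be overturned by 3 withdrawals. A participant who used only one mask has no head-to-head preference, so the both-masks restriction is inherent to that endpoint; only the composite changes.

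**Conclusion.** The concern holds. Followed as written, the plan lets missing ratings depend on the rated outcome, takes no exit rating and has no analysis to show how much this matters. The expected direction is usually toward the mask with more rating-related withdrawals. This is not guaranteed: if one mask's losses are unrelated to its ratings while the other's are related, the shift can run the other way.

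The likely size is small, 2-8% of a true -0.94 at 3 to 5 mask-related withdrawals and 15-22% at the upper bound of 10, under assumed means, SDs and a common withdrawal rule. Larger relative effects, including a change of sign, need the narrower settings shown above. It belongs at the lower end of should-fix: the effect is modest, but the remedy is cheap and one part of it is available only while participants are in the study.

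**What to change.** 1. At the withdrawal contact, invite each willing participant to complete the existing Mask Survey for the mask in use. Clarify the data-collection sentence in the Withdrawal section so that this is plainly allowed. The withdrawal criteria stay unchanged.
2. Keep the completer analysis as planned and add a sensitivity analysis beside it. For ratings, fit a mixed model with mask, period, sequence and random participant to all available ratings, including exit ratings. For overall preference, add a composite in which a mask-related withdrawal counts against that mask, labelled as acceptability.
3. Among all randomized participants, present withdrawals for inadequacy and for mask-related non-use by mask and period, using the sequence and reasons already recorded.

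Cost: one clarified sentence, one optional use of an existing survey, SAP wording, one table split and possibly a check of the payment schedule under Participant Reimbursement. Limits: those who decline the exit survey stay informatively missing, and one-mask participants still give no head-to-head preference.
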